Initial translational studies established that the composition of the fecal microbiota is altered (and butyrate production is reduced) in infants with cow's milk allergy²¹. Feehley et al. demonstrated that there were numerous differentially abundant bacterial operational taxonomic units (OTUs) between healthy and CMA infants or GF mice colonized with the feces of these infants²². Analysis of differentially abundant OTUs that distinguished the CMA and healthy populations in both the human donors and colonized mice. Correlation of ileal taxa with differentially expressed genes in the ileum of healthy-colonized mice identified a Clostridial species, *Anaerostipes caccae*, that mimicked the effects of the healthy microbiota, supporting a causal role for a specific bacterial taxon in protection against food allergy. *A. caccae* is an extremely efficient butyrate producer commonly found in the infant gut but can be identified in adults as well^{23,24}.

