More recently, evidence expands this observation beyond infants. Identification of differentially abundant OTUs in healthy and allergic twins revealed that 84% were in the Clostridia class²⁵. These bacterial OTUs were then correlated with fecal metabolites from nonbiased metabolomic profiling, which identified another potentially protective Clostridial species in healthy twins: *R. bromii*. *R. bromii* is measurable in the feces of many (but not all) adults and is recognized as a keystone species for the degradation of type III resistant starches, like resistant potato starch (RPS)²⁶. *R. bromii* abundance in feces significantly increases upon dietary intervention with RPS^{27,28}. Individuals that do not have detectable *R. bromii* in the feces before beginning a RPS-supplemented diet consume about 40% less total starch than individuals colonized with *R. bromii*, demonstrating that this species alone is responsible for much of the total starch digestion in the colon²⁷. *R. bromii* performs the initial phases of resistant starch digestion, producing intermediate metabolites such as acetate which can then be consumed by butyrate producing bacteria. While *R. bromii* is not capable of producing butyrate itself, a recent report demonstrated that two weeks of RPS consumption by young adults was sufficient to induce detectable increases of butyrate in feces²⁹. This increase in butyrate concentration was greater in individuals who also demonstrated increased fecal abundance of *R. bromii* compared to those with no change. Butyrate concentration was also significantly correlated with changes in the abundance of *Eubacterium rectale*, a well characterized butyrate producing Clostridia²⁹. Interestingly *E. rectale* is one of the few bacterial species detectable in the microbiomes of most healthy individuals worldwide³⁰. Taken together the data suggest that *R. bromii* is a tractable biomarker, associated with a healthy microbiota and increased butyrate production, and responsive to dietary intervention. Interestingly, and in agreement with our hypothesis, the Canadian

CONFIDENTIAL

Healthy Infant Longitudinal Development birth cohort study reported that depletion of *R. bromii* early in life (3 and 12 months of age) is associated with the development of atopy and reduced genetic potential to produce butyrate³¹.

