3.3 Secondary Study Endpoints

The secondary endpoints are as follows:

- To determine the proportion of subjects who experience dose related GI side effects during oral immunotherapy

CONFIDENTIAL

This material is the property of the University of Chicago.
Do not disclose or use except as authorized in writing by the study PI

05.16.2023

- To determine the proportion of subjects who experience hypersensitivity reactions (other than GI) during oral immunotherapy

The exploratory endpoints are as follows:

- To demonstrate the effect of resistant potato starch (RPS) on the fecal microbiome and metabolome
- To determine if gnotobiotic mice colonized with the fecal microbiota of study participants models clinical response
- To evaluate the immunological effects of fiber supplementation in children
 - Change in peanut specific IgE and IgG4 levels
 - Change in peanut skin prick test mean wheal diameter
 - Change in peanut component levels

4 Subject Selection and Withdrawal

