6.5 Visits 6-14 (every 2-4 weeks)

- Interval medical history
- Vital signs
- Physical examination, including height and weight
- Stool sampling (monthly)
- Collection of logs

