7.2 Statistical Methods

Chi-square testing (or non-parametric equivalent) will be used to compare categorical variables. Student's t-test (or non-parametric equivalent) will be used to compare continuous variables. Microbial relationships between samples will be compared using principal coordinate analysis and average-neighbor hierarchical clustering. Welch's t-test will be used to determine significant abundance differences between OTUs.

8 Safety and Adverse Events

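### Section 7.2 screens OTUs by Welch's t-test with no false-discovery control, no named time point and no rule for repeated stools, so false positive taxa are likely

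*Combined protocol and SAP*

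**What the plan says.** The microbiome analysis occupies two sentences of section 7.2, repeated in the Statistical Methodology row of the Study Summary. The first is descriptive: "Microbial relationships between samples will be compared using principal coordinate analysis and average-neighbor hierarchical clustering". The second is the only test: Welch's t-test "will be used to determine significant abundance differences between OTUs". Neither place gives a significance level, a correction across OTUs, a restricted list of taxa, a time point, a baseline adjustment or a way to handle several samples from one child. No other section supplies these.

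Stool is collected at V2 (section 6.2), V4 (6.3), monthly over V6 to V14 (6.5), V15 (6.6) and V16 (6.7). The Schedule of Procedures puts study-arm randomisation at V3, so the V2 stool is a true baseline.

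The status of the question differs between sections. Section 3.3 lists it among the exploratory endpoints: "To demonstrate the effect of resistant potato starch (RPS) on the fecal microbiome and metabolome". Section 2.2 makes the influence of the prebiotic on the microbiome and metabolome a secondary objective.

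**The concern.** A separate t-test on each of many taxa produces some small p-values by chance. Without error control across taxa, a list of significant OTUs cannot be told apart from noise. Welch's test relaxes the assumption of equal variances but still needs independent observations. Serial stools from one child are not independent, and section 7.2 does not say which stools enter the test.

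What is at stake is the mechanism. Section 1.1 predicts that RPS will expand protective bacteria and thereby improve the outcome of peanut oral immunotherapy (POIT). A taxon list that would probably appear even if RPS had no effect cannot support or refute that prediction.

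**Working it through.** The plan states no error rate, OTU count or power for this analysis, so there is no figure of its own to reproduce.

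**Inputs from the documents.** 30 children (7.1), randomised 1:1 (Study Summary), so 15 per arm. V6 to V14 are 9 visits, 2 to 4 weeks apart (6.5): 8 intervals, spanning 8 × 2 = 16 to 8 × 4 = 32 weeks, or about 4 to 9 monthly stools. Adding V2, V4, V15 and V16 gives about 8 to 13 per child. Leaving out V2 gives 7 to 12 after baseline.

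**Assumed, because the documents are silent.** Two-sided α = 0.05 (0.01 as a low case); m = 20 to 500 OTUs; within-child correlation (ICC) 0.3 to 0.7. The test is read as a comparison of arms for each OTU, the only sensible reading of the sentence.

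**Step 1: one sample per child, RPS without effect.** Expected false positives are m × 0.05: 1 for m = 20, 5 for m = 100 and 25 for m = 500. For independent OTUs, P(at least one) = 1 − 0.95^m. The other rows were simulated (1,000 replicates each, 15 per arm).

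| P(at least one false positive) | m = 20 | m = 100 | m = 200 |
|---|---|---|---|
| Independent OTUs (formula) | 64% | 99.4% | >99.9% |
| Blocks of 20 OTUs, correlation 0.5 | 42% | 92% | 99.6% |
| All OTUs correlated 0.5 | 42% | 76% | 88% |
| Skewed, zero-heavy relative abundances | 34% | 82% | 97% |

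In the last row Welch's test is conservative, at about 1.8% per test, so the expected number of false positives is about 1.7 at m = 100 and 3.6 at m = 200. With only 10 children per arm, the 82% becomes 70%. At α = 0.01 with independent OTUs, 1 − 0.99^m gives 63% at m = 100, 87% at m = 200 and 99.3% at m = 500.

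**Step 2: if k stools per child were pooled as independent.** The variance of the arm difference is understated by the factor D = 1 + (k − 1) × ICC, so the actual error per OTU is about 2 × [1 − Φ(1.96/√D)].

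- k = 7, ICC 0.3: D = 2.8, 1.96/1.673 = 1.171, error 24%.
- k = 12, ICC 0.7: D = 8.7, 1.96/2.950 = 0.665, error 51%.

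Simulation at k = 11 (20,000 replicates) gave 33%, 43% and 50% at ICC 0.3, 0.5 and 0.7. The formula gives 33%, 42% and 49%.

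**Step 3: if each visit were tested separately.** The simulated chance of at least one false hit for a single OTU was 21% to 33% over 9 visits and 23% to 38% over 11 visits.

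**Step 4: under error control.** With one value per child and Benjamini-Hochberg at q = 0.05, the simulated chance of reporting any taxon when RPS does nothing was about 3% to 6% for normal data, independent or correlated. It was 0.6% or less for skewed, sparse data. Averaging each child's stools before testing brought the error per OTU back to 4.7% to 5.1%.

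**The case against.** The best defence is that this is an exploratory endpoint in a 30-child pilot, where formal error control is often relaxed, and that a short plan which omits a detail has not thereby chosen the worst option. Much of this stands. The primary endpoint's error rate is untouched. The level, the OTU count and the within-child correlation are all assumptions. Fecal butyrate, being continuous, is already covered by the general t-test sentence in 7.2, although it is not singled out.

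Exploratory status is not a full answer. Section 2.2 ranks the microbiome as a secondary objective, section 3.3 sets out to demonstrate an effect, and 7.2 intends to declare differences significant.

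A reader might also infer more than the documents support:

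- That false positives are certain. They are likely to very likely, depending on the number and correlation of OTUs and the level used.
- That the plan prescribes an unadjusted level, pools all stools or discards the V2 sample. It specifies none of these. The figures in Step 2 show what the text permits, not what is planned.
- That a false taxon list would misdirect the mouse work. Section 3.3 describes colonising mice with participants' fecal microbiota and does not make this depend on an OTU list. No section ties the OTU results to a later trial.
- That the background points to a single target species. Section 1.1 names both A. caccae and R. bromii as candidates.

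**Conclusion.** The omission is clear: 7.2 sets up a significance screen across OTUs without a level, error control, a time point or a unit of analysis, in a design with repeated stools. Its consequence is conditional. With 100 or more OTUs, two-sided 0.05, one sample per child and 15 children per arm, at least one false finding under no effect has probability of about 76% to over 99%. Up to 5 are expected per 100 OTUs, or about 2 if abundances are skewed and sparse. Fewer OTUs or a stricter level lowers this, and pooled or visit-by-visit testing raises it. The point should be corrected because a stated objective cannot be answered reliably as written. It is not a threat to the trial's main result.

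**What to change.** In section 7.2, and in the matching row of the Study Summary:

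1. State that arms are compared taxon by taxon, using either one value per child at a named visit or a mixed model with a child random effect. V4 is a natural choice of visit, since it follows 30 days of RPS or placebo and is the day POIT starts.
2. Enter the V2 value as a covariate.
3. Apply Benjamini-Hochberg at a stated q, for example 5%, across all taxa and contrasts tested.

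Optionally, name R. bromii abundance and fecal butyrate as planned tests ahead of the screen, and say how those two are adjusted. Section 1.1 ties both to RPS and says that R. bromii "is a tractable biomarker, associated with a healthy microbiota and increased butyrate production". The authors should then also say whether A. caccae belongs with them. Log-ratio transformation, arm-by-visit terms and PERMANOVA alongside the ordination are reasonable additions but are not needed to cure the problem.

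The cost is SAP wording and analyst time, and fewer taxa will be called significant. No visit or sample is added.

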8.1 Definitions

Unanticipated Problems Involving Risk to Subjects or Others

Any incident, experience, or outcome that meets all of the following criteria:

- Unexpected in nature, severity, or frequency (i.e. not described in study-related documents such as the IRB-approved protocol or consent form, the investigators brochure, etc)
- Related or possibly related to participation in the research (i.e. possibly related means there is a reasonable possibility that the incident experience, or outcome may have been caused by the procedures involved in the research)
- Suggests that the research places subjects or others at greater risk of harm (including physical, psychological, economic, or social harm).

Unanticipated Serious Adverse Event

An Unanticipated Effect is any serious adverse effect on health or safety, or any life-threatening problem or death caused by, or associated with the study food, if that effect, problem, or death was not previously identified in nature, severity, or degree of incidence in the investigational plan or application (including a supplementary plan or application), or any other unanticipated serious problem associated with a study food that relates to the rights, safety, or welfare of subjects.

Serious Adverse Event

Any injury or illness that is any one of the following:

- death
- life-threatening (at the opinion of the investigator an immediate risk of death occurred)
- results in permanent impairment of a body function or permanent damage to body structure

CONFIDENTIAL

This material is the property of the University of Chicago.
Do not disclose or use except as authorized in writing by the study PI

05.16.2023

- necessitates medical or surgical intervention to preclude permanent impairment of a body function or permanent damage to a body structure

Adverse Event

An **adverse event** (AE) is any symptom, sign, illness or experience that develops or worsens in severity during the course of the study. Intercurrent illnesses or injuries will be regarded as adverse events. Abnormal results of diagnostic procedures (including DBPCFC) are considered to be adverse events if the abnormality:

- results in study withdrawal
- is associated with a serious adverse event
- leads to additional treatment other than epinephrine, antihistamines and corticosteroids or to further diagnostic tests
- is considered by the investigator to be of clinical significance

Adverse Event Severity

The investigator will assign severity grades to adverse events. Adverse events will be graded using the CoFAR grading system as follows:

Grade 1 (mild): transient or mild discomforts (<48 hours); no or minimal medical intervention/therapy required. For allergic reactions, these symptoms may include pruritus, swelling, or rash, abdominal discomfort or other transient symptoms.

Grade 2 (moderate): symptoms that produce mild to moderate limitation in activity that may require some assistance; no or minimal intervention/therapy is required; hospitalization is possible. For allergic reactions, these symptoms may include persistent hives, wheezing without dyspnea, abdominal discomfort/increased vomiting or other symptoms

Grade 3 (severe): marked limitation in activity that usually requires some assistance usually; medical intervention/therapy required; hospitalization is possible. For allergic reactions, symptoms may include bronchospasm with dyspnea, severe abdominal pain, throat tightness with hoarseness, transient hypotension among others. Parenteral medications are usually indicated.

Grade 4 (life-threatening): extreme limitation in activity that requires significant assistance; significant medical/therapy or intervention is required; hospitalization is probable. Symptoms may include persistent hypotension and/or hypoxia with resultant decreased level of consciousness associated with collapse and/or incontinence or other life threatening symptoms.

Grade 5 (death): death

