8.3 Reporting of Adverse Events and Unanticipated Problems

Researchers will submit reports of the following problems within 10 working days from the time the investigator becomes aware of the event:

Any adverse event that occurs any time during or after the research study, which in the opinion of the principal investigator is:

- **Unexpected** (An event is “unexpected” when its specificity and severity are not accurately reflected in the protocol-related documents, such as the IRB-approved research protocol, any applicable investigator brochure, and the current IRB-approved informed consent document and other relevant sources of information, such as product labeling and package inserts.)

AND

- **Related** to the research procedures (An event is “related to the research procedures” if in the opinion of the principal investigator or sponsor, the event was more likely than not to be caused by the research procedures.)

The above will be completed regardless of whether the event is serious or non-serious, on-site or off-site

Protocol Deviations

Any protocol deviations initiated without the The University of Chicago IRB approval that may affect the scientific soundness of the study, or affect the rights, safety, or welfare of study subjects, will be reported to the IRB as soon as a possible, but no later than 5 working days of the protocol deviation.

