8.4.2 Overall Stopping Rules

This study will be suspended at any time if a study related death occurs in a subject on active therapy or upon the hospitalization of the second of two study related hospitalizations. If the study is suspended, screening, enrollment and POIT increases will immediately stop but active subjects will continue on current dosing unless otherwise directed by the FDA. The study and POIT dose escalation will not resume until discussed with the DSMB and FDA.

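### The SAE definition omits hospitalization, and a related admission for an expected reaction has no timed report, although Section 8.4.2 suspends the study at the second related hospitalization

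*Combined protocol and SAP*

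**What the plan says.** Section 8.1 defines a serious adverse event as "Any injury or illness that is any one of the following" and gives four criteria: death; a life-threatening event in the investigator's opinion; an event that "results in permanent impairment of a body function or permanent damage to body structure"; and one that "necessitates medical or surgical intervention to preclude permanent impairment of a body function" or damage to a body structure. Hospitalization is not a criterion.

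The severity scale in the same section says of Grade 2 events that "no or minimal intervention/therapy is required; hospitalization is possible". It repeats that hospitalization is possible at Grade 3 and calls it probable at Grade 4.

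Section 8.2 has all adverse effects recorded at once in the source document and the CRF. Its minimum data set includes a description of the event, its association with study treatment, and whether and why it is serious. Hospitalization is not an item. The specific questioning at each contact is about effects of the fiber supplement.

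Section 8.3 requires a report "within 10 working days from the time the investigator becomes aware of the event" for an adverse event that is both unexpected and related, whether or not it is serious.

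Section 8.4.1 has a DSMB review safety data continually and refers to a charter for details.

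Section 8.4.2 has two triggers. The first reads: "This study will be suspended at any time if a study related death occurs in a subject on active therapy". The second takes effect "upon the hospitalization of the second of two study related hospitalizations". On suspension, screening, enrollment and POIT dose increases stop at once.

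**The concern.** A rule that suspends a trial on a count of two needs each counted event to be recognized as countable and passed on promptly to those who apply the rule. Here the event counted in 8.4.2 does not by itself make an event serious in 8.1, is not a field in 8.2, and is not a ground for a report in 8.3. The participants are children receiving their allergen, largely at home, and the maintenance visits are three months apart (Sections 6.6 and 6.7). If an admission between visits is first recorded at the next visit, the immediate stop that 8.4.2 intends would come late. The reported SAE count would also leave out admissions that resolve and meet none of the four criteria.

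**Working it through.** No arithmetic applies: the point rests on no rate, power or sample size, and the plan states no figure to reproduce. The check is to follow each kind of suspension event through 8.1, 8.3 and 8.4.2.

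| Event | SAE under 8.1? | Timed report under 8.3? | Counts under 8.4.2? |
|---|---|---|---|
| Related death on active therapy | Yes | Yes, if unexpected | Yes, one is enough |
| Related admission, unexpected | Only if another criterion is met | Yes, 10 working days, whatever its seriousness | Yes, toward two |
| Related admission, expected reaction, another SAE criterion met | Yes | No | Yes, toward two |
| Related admission, expected reaction, no other criterion met | No | No | Yes, toward two |

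1. *Can the last row occur?* Yes. Section 1.5 (Risks Associated with POIT) lists systemic allergic reactions and anaphylaxis as a side effect, so an admission for one can fail the unexpected test in 8.3. The grading scale allows hospitalization at Grades 2 and 3, so an admitted child need not have had a life-threatening event.

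2. *Does 8.2 capture it?* Only in part. The event should be recorded and described, but nothing requires the description to mention an admission. The seriousness field does not pick it up, because admission is not a reason for seriousness. The active questioning does not name POIT reactions.

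3. *Does 8.4.1 capture it?* The DSMB sees safety data continually. Its stated ground for halting is a substantial imbalance in adverse events, which is a different test from a count of two admissions. No supplied text says that admissions are sent to it as they occur.

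4. *Does the timing fit?* The only adverse-event clock is 10 working days, and it does not start in the last two rows. Section 8.4.2 calls for an immediate stop.

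5. *Is study-related defined?* Not in 8.4.2. Section 8.1 treats an event as possibly related when there is a reasonable possibility of causation. Section 8.3 asks whether the research was more likely than not the cause. The same admission could be related under one test and unrelated under the other.

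**The case against.** The strongest reply is that the plan already has several routes. Death is an SAE. Section 8.3 does not depend on seriousness, so an unexpected related admission must be reported within 10 working days even though it is not an SAE on that ground. Some admitted reactions will meet another SAE criterion. Section 8.2 has adverse effects recorded immediately, Section 9.2 counts hospital records as source documents, and interval histories and dosing logs are collected during treatment. The investigator oversees safety (8.4), and the DSMB reviews data continually under a charter that may contain a forwarding rule.

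All of this stands, and it rules out two stronger readings. A reader might infer that the events that suspend the trial have no reporting route at all; the first two rows of the table show otherwise. A reader might also infer that the missing SAE criterion is what removes the timed report. It is not: 8.3 turns on unexpected plus related, so adding hospitalization to the SAE list alone would create no timed report.

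The reply does not reach the related admission for an expected reaction. Recording in a CRF is not timely notice to those who apply 8.4.2, and the charter cannot be checked here.

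**Conclusion.** The point holds in a limited form. Under the supplied text, a related admission for an expected POIT reaction that meets no other SAE criterion counts toward an immediate suspension, yet is classed as non-serious and has no timed report. Sections 8.1, 8.2, 8.3 and 8.4.2 need to be reconciled.

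Its size cannot be put in numbers. The trial plans 30 children and the trigger is the second admission, but the documents give no expected admission rate. A reader might infer that the final SAE count will be wrong. Against the protocol's own definition it would be correct; it would only leave out admissions that the suspension rule treats as important. SAE frequency is not a listed endpoint, so the planned efficacy and side-effect comparisons are not affected.

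The conclusion assumes that the investigator would read anaphylaxis after a POIT dose as expected, because Section 1.5 describes it, and that the DSMB charter has no forwarding rule of its own. If the charter has one, the remaining issue is mainly consistency of definitions.

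**What to change.** Reconcile the four sections:

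- **8.1:** add inpatient hospitalization to the SAE criteria. The existing 8.2 field for the reason an event is serious will then capture it, so no separate data item is needed.
- **8.2:** extend the specific questioning at each contact to POIT reactions as well as effects of the supplement.
- **8.3:** state that every study-related hospitalization, expected or not, is reported to the DSMB when the investigator learns of it. This is the change that closes the timing gap. If the charter already says so, cite it here.
- **8.1, 8.3 and 8.4.2:** use one definition of study-related.

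The suspension threshold and all dosing rules stay as they are. The cost is a few lines of protocol text, a few more SAE forms, and a slightly higher reported SAE count.
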